6.5.3.8 Cervical smear

Cervical smears findings will be summarized by treatment group and visit with a frequency table.

A listing will be provided with cervical smear results for each subject.

6.5.3.9 Vital signs

Vital signs (heart rate, systolic blood pressure and diastolic blood pressure, and weight) will be summarized by treatment group and visit grouped by TP, including change from baseline where appropriate, using descriptive statistics. Boxplot for absolute values at each visit will be presented by treatment group. The time course by visit and by treatment group will be shown using line plots depicting the mean and 95% CI (two-sided).

For safety closeout visit blood pressure will be measured as triplicates, mean value of triple measurements will be reported in tables.

6.5.3.10 Liver monitoring

Hepatic safety will be evaluated based on the following time intervals:

- BL/Post baseline
- Intervals A

The following parameters will be investigated in addition to the standard lab presentations:

- aspartate aminotransferase (U/L) (AST),
- alanine aminotransferase (U/L) (ALT),
- alkaline phosphatase (U/L) (AP),
- bilirubin in serum (mg/dL).

In case of more than one measurement within a time interval, a worst case approach will be used, i.e. the maximum value will be used for calculations.

Frequency tables presenting number and percentage of subjects fulfilling the following criteria will be produced:

- Normal, $>1xULN - <3xULN$, $\geq 3xULN - <5xULN$, $\geq 5xULN - < 8xULN$; $\geq 8xULN - <10xULN$; $\geq 10xULN - <20xULN$, $\geq 20xULN$ of ALT and AST respectively
- $\leq 1xULN$; $1xULN - 2xULN$; $\geq 2xULN$ of Bilirubin
- $\leq 1xULN$; $1xULN - 1.5xULN$, $\geq 1.5xULN$ of AP
- $\geq 3\times$, $5\times$, $8\times$, $10\times$, and $20\times ULN$ of ALT
- $\geq 3\times$, $5\times$, $8\times$, $10\times$, and $20\times ULN$ of AST
- $\geq 3\times$, $5\times$, $8\times$, $10\times$, and $20\times ULN$ of ALT or AST
- $>1xULN$, $> 2\times ULN$ of bilirubin
- >1.5 of AP
- $>3xULN$ of ALT or AST accompanied by $>1.5xULN$ Bilirubin (any time point)
- $>3xULN$ of ALT or AST accompanied by $>2 xULN$ in Bilirubin (any time point)

Combined parameters based on Hy's Law criteria

Frequency tables will be provided for

- $\geq 3\times ULN$ of ALT or AST accompanied by $\geq 2\times ULN$ of bilirubin (within 30 days afterwards).
The event will be assigned to the time interval of the ALT/AST elevation.

Time to event analysis

Kaplan Meier analysis will be performed by time intervals as described above. Time to ALT $> 3xULN$ after start date of the respective time interval will be presented. If no such an increase is observed within the time interval, this is considered a censored observation and the end date of the time interval will be used as date. Tables with number of subjects under risk, cumulative number of ALT $>3xULN$ increases, and estimated probability of increase including 95% confidence intervals within the respective time interval will be presented per 28-day intervals. Furthermore, Kaplan Meier plots will be provided.

Figures and individual subject presentations

An

- eDISH plot (maximum of ALT and AST within time interval × maximum of total bilirubin within 30 days thereafter) and a
- Scatter plot (maximum ALT within time interval x maximum AST within time interval)

will be provided by time interval as described above.

Individual subject presentations

For subjects meeting the following criteria, figures on individual time courses will be presented:

- ≥ 3 x ULN of ALT at any time point

The following lab parameters will be presented: ALT, AST, bilirubin, and AP relative to ULN over time within one figure per subject on absolute scale. It will be indicated within the figure on which days study drug was taken (i.e. start and stop of treatment periods). Furthermore, listings will be provided with laboratory information on liver related parameters, i.e. ALT, AST, bilirubin, AP (relative to upper limit of normal).

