Exit examination	BL, last value within interval																		Exit examination (Start: EoT -7 days); last value within this interval								

Abbreviations: BL: Baseline, TP: Treatment Period, BR: Break (not applicable for Treatment group B), FUP: Follow-up, d: days, m: months.

Treatment periods and breaks will be identified as described above. Baseline/Pre-treatment phase starts with the date of informed consent and ends on the day before the start of the Treatment phase.

The Treatment phase starts and ends with the reference start and end date. The FUP phase starts on the day after the end of the treatment phase and ends on the maximum of the last date at which a visit took place (visit end date), and the “last visit” as collected on the eCRF page. For patients who did not complete the planned schedule of TPs, a break period will be defined after the end of the last TP, as described in the previous subsection ‘Break period’. This break period will be followed by the FUP.

Baseline, Treatment phase, FUP phase, TPs and breaks are subdivided into subsequent periods of different lengths (28, 84, or 168 days). Exit examination time intervals include the baseline measurement, i.e. the last non-missing value before reference start date, and the exit examination which is defined as the last non-missing value at or after the reference end date – 7 days, which is per definition the safety closeout visit for subjects who perform this visit.

For treatment group B, consecutive TPs (84-day time intervals) in the treatment phase will be used for intervals B and intervals C. Each TP will be subdivided into subsequent consecutive 28-day periods for intervals D. For intervals for assessing AEs in the treatment phase, consecutive TPs will be ended at day 60 after the reference end date. For the assessment in the follow-up phase, same rules will be used as VPR treatment groups.

Details on time intervals for AE presentation are given in Section 6.5.3.5.

Details on time intervals for BMD presentation are given in Section 6.5.1.

Break period

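### The follow-up Kaplan-Meier analysis of ALT >3xULN has no at-risk condition at entry, so an elevation persisting from treatment into a follow-up sample counts as an event in both phases

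*SAP*

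**What the plan says.** SAP section 6.5.3.10 names two sets of intervals for hepatic safety: baseline/post-baseline, and Intervals A, which Figure 4-1 divides into treatment phase and FUP phase. For the time-to-event part it states: "Kaplan Meier analysis will be performed by time intervals as described above". The clock restarts in each interval, because time to ALT >3xULN is measured "after start date of the respective time interval will be presented. If no such an increase is observed within the time interval", the subject leaves the curve without an event. The wording for that case is: "this is considered a censored observation and the end date of the time interval will be used as date". Event and censored at interval end are the only two outcomes defined.

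The outputs, per 28 days, give the risk set and the running event count: "Tables with number of subjects under risk, cumulative number of ALT". The events counted there are called increases. The same tables also give the "estimated probability of increase including 95% confidence intervals within the respective time interval".

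Section 4.5 fixes the boundary between the phases. On the treatment side it says: "The Treatment phase starts and ends with the reference start and end date". For follow-up the rule is: "The FUP phase starts on the day after the end of the treatment phase". The reference end date is the last study drug intake for vilaprisan and the end-of-treatment visit for group B. There is no gap between the phases.

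**The concern.** A Kaplan-Meier probability of an increase describes subjects who are below the threshold at time zero and then cross it. The rule in section 6.5.3.10 asks only whether a value above 3xULN occurs after the interval starts. For the treatment phase and for FUP separately, a raised value that has not yet come down satisfies it twice: when it first appears on treatment, and again when it is next sampled after treatment ends. The second count is not a new crossing, and the value may even be falling.

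The reason to split treatment from follow-up is to see whether liver elevations track drug intake, and liver disorders are an adverse event of special interest in section 6.5.3.5. A FUP curve that includes elevations begun on treatment answers that question less cleanly than its label suggests. When events are few, one or two carried-over cases can make up most of the FUP count.

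**Working it through.** The SAP gives no event count, rate or sample size for this analysis, so there is no planned figure to reproduce. The check has two parts.

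**1. The rule applied to example ALT series (values invented for illustration).**

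- 4.2xULN on treatment, 3.6xULN on FUP day 7: event in the treatment phase, and event again in FUP on day 7.
- 4.0xULN on treatment, 2.5xULN at the first FUP sample and lower afterwards: event in the treatment phase only, censored in FUP.
- Normal on treatment, 3.4xULN on FUP day 28: event in FUP only.

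The first series is the problem case. The double count arises when an elevation is still above 3xULN at a FUP measurement. It cannot arise in the post-baseline interval, which does not split treatment from follow-up.

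**2. Size, under assumed counts.** Let N be the subjects entering FUP, k those carried over above 3xULN, and m those with a new crossing. Ignoring censoring before the events, the Kaplan-Meier probability reduces to a proportion:

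- rule as written: (k + m) / N
- new crossings only: m / (N − k)

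| N | k | m | As written | New crossings only |
|---|---|---|---|---|
| 200 | 0 | 1 | 1/200 = 0.50% | 1/200 = 0.50% |
| 200 | 1 | 1 | 2/200 = 1.00% | 1/199 = 0.50% |
| 200 | 2 | 0 | 2/200 = 1.0% | 0/198 = 0% |
| 200 | 2 | 1 | 3/200 = 1.5% | 1/198 = 0.51% |
| 200 | 5 | 1 | 6/200 = 3.0% | 1/195 = 0.51% |
| 100 | 2 | 0 | 2/100 = 2.0% | 0/98 = 0% |
| 100 | 2 | 1 | 3/100 = 3.0% | 1/98 = 1.02% |

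N, k and m are all assumptions. With k = 0 the two estimates are identical.

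**Comparison within the SAP.** Section 6.5.3.4 assigns ovarian cyst episodes, and adverse events related to them, to the interval in which they start. Section 6.5.3.5 makes a continuing adverse event a second event in a later phase only if it worsens. The liver section has one assignment rule, "The event will be assigned to the time interval of the ALT/AST elevation", and it belongs to the Hy's Law frequency table. It does not address an ALT elevation that spans two intervals.

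**The case against.** The strongest reply is that the SAP nowhere says such subjects stay in the risk set. It speaks of subjects under risk and of increases, and a programmer might take those words to exclude anyone already above the threshold. That is fair as far as it goes: the point rests on the literal event and censoring rule and on the absence of an entry condition. But the text defines the event only as ALT >3xULN after the interval start and provides no not-at-risk status, so a program written from it would count these subjects.

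Second, section 6.5.3.10 takes the worst value per interval for its tables, and individual time courses are planned for every subject with ALT ≥3xULN, with treatment periods marked. A careful reader could identify each carried-over case. This stands and limits the harm, but those figures do not correct the tabulated probability or its confidence interval. A worst-value frequency table makes no claim about onset, whereas the Kaplan-Meier output does.

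Third, a reader might infer more than the SAP supports:

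- *That on-treatment elevations in general are counted again.* Only those still above 3xULN at a FUP sample are.
- *That a subject entering FUP with raised ALT could never have a new increase.* She could fall below the threshold and rise again, so excluding her at entry needs a place to report that.
- *That the plan will show a spurious post-treatment excess on vilaprisan.* This would need carry-over to occur, and to occur unequally between groups. The SAP gives no data on either.
- *That >3xULN is an error because the ALT frequency tables and individual figures use ≥3xULN.* Two combined ALT/AST-with-bilirubin criteria in the same section also use >3xULN, and counts can differ only at exactly 3xULN.

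**Conclusion.** The point holds in limited form. As written, the FUP Kaplan-Meier analysis of ALT >3xULN has no at-risk condition at entry, so an elevation persisting from treatment into a FUP sample is an event in both phases. The FUP estimate is then not the probability of an increase that its label claims.

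The size cannot be derived from the SAP. It is zero without carry-over; with an assumed 200 entering FUP and 2 carried over, it is 1.0% against 0% with no new rise, or 1.5% against 0.51% with one. The analysis is descriptive, sits among the other safety variables and drives no decision rule. This is a worthwhile clarification, not a threat to the trial's conclusions.

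**What to change.** In section 6.5.3.10, state that the FUP Kaplan-Meier analysis counts new crossings only. At FUP start, limit the risk set to subjects whose last ALT at or before the reference end date does not exceed the analysis threshold. Show the number entering FUP with an ongoing elevation on a separate line, and report any later fall and renewed rise among them there. Leave the post-baseline curve unchanged as the overall total.

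The cost is a short addition to the SAP and one condition in the program, using data already collected. There are two small downsides. The few subjects with ongoing elevation leave the FUP curve. An on-treatment rise first sampled after the last tablet would still count as a FUP event, and a footnote should say so.

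Optionally, use one threshold convention, either > or ≥3xULN, for the Kaplan-Meier analysis and the ALT frequency tables so that their counts agree.

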With the implementation of protocol amendment 9 (Version 6.0), no further subjects were recruited. Subjects that started to a regimen with 3-months treatment courses should finish the treatment course as planned. Subjects that started to a regimen with treatment courses of 6 months duration should finish the first 3 months, if they are currently in the first 84 days of that treatment course, finish the second 3 months, if they are currently beyond day 84 of the treatment course. Thus, with the implementation of protocol amendment 9 and the originally foreseen study design outlined in [Figure 3-1](#) is not applicable anymore for vilaprisan groups. Subjects in treatment group B can continue the study course following the current valid version of the protocol.

With the implementation of Protocol Amendment 10 (version 7.0), this study design as outlined in [Figure 3-1](#) is no longer valid. No subjects will receive further study drug treatment. All subjects who were randomized and started treatment before the temporary pause were asked to have a comprehensive safety evaluation (with particular focus on endometrial, adrenal and skin safety) performed. This also applies to subjects who have completed or discontinued the study before or during the temporary pause, provided they have taken at least one dose of study medication.

Likewise, subjects randomized to treatment group B who are still in the study will be asked to undergo these procedures.

At the time study treatment was terminated, no subjects in subgroup 2 had reached the second year of treatment. Therefore, the statistical analysis will include patients from both subgroups without any distinction.

Figure 3-1 Design overview

Subgroup 1 (about 1 year of treatment)

A1	SCR up to 90 days	RND	12 wk trt	B	12 wk trt	B	12 wk trt	B	12 wk trt	24 wk FUP
A2	SCR up to 90 days	RND	24 wk trt		B	B	24 wk trt		24 wk FUP	
A3	SCR up to 90 days	RND	12 wk trt	B	B	12 wk trt	B	B	12 wk trt	24 wk FUP
B	SCR up to 90 days	RND	Symptomatic nonhormonal medical treatment as determined by the investigators and/or watch and wait						24 wk FUP	

Subgroup 2 (about 2 years of treatment)

A1	SCR up to 90 days	RND	12 wk trt	B	12 wk trt	B	12 wk trt	B	12 wk trt	B	12 wk trt	B	12 wk trt	B	12 wk trt	B	12 wk trt	12 wk FUP
A2	SCR up to 90 days	RND	24 wk trt		B	B	24 wk trt		B	B	24 wk trt		B	B	24 wk trt		12 wk FUP	
A3	SCR up to 90 days	RND	12 wk trt	B	B	12 wk trt	B	B	12 wk trt	B	B	12 wk trt	B	B	12 wk trt	B	B	12 wk FUP

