6.5 Safety

The safety analysis will be performed on the observed safety data for the safety analysis population.

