6.5.3.6 Laboratory parameters

For immunology and coagulation parameters Intervals ‘BL/Post baseline’ will be used, while for all other laboratory measurements the following time intervals will be considered:

- Intervals C (according to Figure 4-1)

The tabulation will follow in principle the Bayer Global Standard Tables catalogue (currently V 4.0 default), with the necessary modifications like for time interval presentation instead of visit presentation.

The maximum or minimum measurement within the time interval will be used for calculations, following a worst-case approach (for details please refer to Appendix 2). Scheduled as well as unscheduled measurements will be considered.

Central as well as local lab measurements are available. Summary statistics will be provided based on central lab. Local lab measurements will be listed.

Values below the lower limit of quantification (LLOQ) will be set to LLOQ/2.

Values above the upper limit of quantification (ULOQ) will be set to ULOQ.

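### Time to ALT >3xULN is censored at the end of the time interval rather than at the last ALT sample, so the Kaplan-Meier probability is equal to or below the correct value

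*SAP*

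**What the plan says.** Section 6.5.3.10 of the SAP (Liver monitoring, time-to-event analysis) plans a Kaplan-Meier analysis for the post-baseline interval and for Intervals A, which are the Treatment phase and the FUP phase. Time to ALT >3xULN "after start date of the respective time interval will be presented". For a subject without such a rise, "this is considered a censored observation and the end date of the time interval will be used as date". Numbers at risk, cumulative events and the estimated probability with its 95% confidence interval "within the respective time interval will be presented per 28-day intervals".

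Section 4.5 fixes the interval ends:

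- **Treatment phase:** "The Treatment phase starts and ends with the reference start and end date". Under Table 4-1 the reference end date is the last intake for vilaprisan and the EoT visit for group B, with diary or last-visit dates as fallbacks.
- **FUP phase:** it "ends on the maximum of the last date at which a visit took place (visit end date") and the last visit recorded on the eCRF page.

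Neither end depends on a blood sample. Section 6.5 adds: "The safety analysis will be performed on the observed safety data for the safety analysis population". Section 6.5.3.6 says of laboratory data in general: "Summary statistics will be provided based on central lab. Local lab measurements will be listed".

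**The concern.** A rise in ALT can be detected only when ALT is measured. A subject whose last sample precedes her interval end has unknown ALT status from then on, yet the rule keeps her in the risk set as event-free. A subject with no ALT in the interval is counted as event-free throughout it. For a liver safety signal this error runs in the non-conservative direction.

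The trial's history makes such gaps possible. Section 3 calls treated subjects back for a comprehensive safety evaluation, and "This also applies to subjects who have completed or discontinued the study before or during the temporary pause". A late recall visit extends the FUP and post-baseline intervals. If no ALT is drawn at that visit, the added time is unsampled.

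The SAP handles other endpoints differently. In section 4.5, a subject with no documented start of bleeding is censored no later than her last available diary date, and censoring for onset of amenorrhea follows the available pictogram data.

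**Working it through.** The SAP states no figure for this analysis, so there is none to reproduce. The check covers the direction of the bias first, and then its size under stated assumptions.

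**Direction.** With d_j events and n_j subjects at risk at event time t_j, the estimated probability is

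F = 1 − ∏ (1 − d_j / n_j).

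The events and their dates are the same under both censoring rules; only n_j changes. An event-free subject stays at risk to her interval end under the SAP rule and to her last ALT under the alternative. The interval end is never the earlier of the two, so n_j(SAP) ≥ n_j(last ALT) at every t_j. Each d_j / n_j, and therefore F, is equal or lower under the SAP rule. It is strictly lower when an event falls after some event-free subject's last ALT and no later than her interval end. In 1000 random data sets the SAP-rule estimate never exceeded the other.

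**Worked example (invented data).** There are 100 subjects and an interval of 364 days, with events on Days 28, 84 and 168. Thirty event-free subjects have their last ALT on Day 56, and the other 67 are sampled to the end.

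| Event day | At risk, SAP rule | At risk, last-ALT rule |
|---|---|---|
| 28 | 100 | 100 |
| 84 | 99 | 69 |
| 168 | 98 | 68 |

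- SAP rule: 1 − (99/100)(98/99)(97/98) = 3.0%.
- Last-ALT rule: 1 − (99/100)(68/69)(67/68) = 3.9%.

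**Simulation (all rates assumed).** The interval is about one year (364 days with ALT every 28 days, 336 days with ALT every 84 days), and the true probability is 2% or 5%. In a share f of subjects the last ALT falls at a uniformly distributed earlier visit, possibly the start, while the interval continues. Each setting has 400,000 subjects. The table gives the ratio of the SAP-rule estimate to the last-ALT estimate; to two decimals it is the same for both true probabilities except where two values are shown.

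| f | ALT every 28 days | ALT every 84 days |
|---|---|---|
| 0 | 1.00 | 1.00 |
| 10% | 0.95 | 0.94 |
| 20% | 0.89 | 0.88 |
| 30% | 0.84 | 0.81 |
| 50% | 0.73 | 0.69 |

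For example, with f = 30%, a true probability of 5% and 28-day sampling, the estimates are 4.2% and 5.0%. Over f = 10% to 50% the relative understatement is about 5% to 31%. With no gap the two rules agree exactly.

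**Where gaps can arise.** In the Treatment phase the interval closes at the subject's own last intake or EoT visit, so the gap is likely short. In the FUP and post-baseline intervals it may be longer, because the end is the last visit of any kind.

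**The case against.** **Interval ends are subject-specific.** A reader might infer that early dropouts are carried event-free to a common study end. Section 4.5 does not support this: a subject whose visits stop early also has an early FUP end. The excess is only the gap between her last ALT and her own interval end. This objection stands and limits the size.

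**A large bias needs a long gap.** A reader might construct a large figure. With an assumed one-year risk of 4%, and 20%, 40% or 60% of subjects last sampled on Day 168 of a 365-day interval, the estimates are 3.6%, 3.1% and 2.7%, which is 11%, 21% and 32% too low. The arithmetic is right, but a gap of 365 − 168 = 197 days in so many subjects is nowhere described in the SAP and is implausible during treatment.

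**A difference between arms is not shown.** The recall in section 3 is asymmetric: vilaprisan subjects who took at least one dose are called back even if they had finished or discontinued, whereas group B is asked only if still in the study. One might infer unequal bias. That would follow only if recall visits lacked ALT, which the SAP does not settle. Section 6.5.3.11 lists laboratory testing at closeout without naming the analytes. If ALT is drawn there, both rules nearly coincide, and what remains is infrequent sampling between visits, which moving the censoring date does not address.

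**The consequence is limited.** This is one descriptive display among the other safety variables, with no test or threshold attached. The frequency tables, combined ALT/AST-bilirubin tables, eDISH and scatter plots, individual time courses and listings do not use the rule. No ALT case is lost.

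**Observed data only.** The restriction in section 6.5 could be read as excluding subjects without ALT. It does not say so for this risk set, and it does not move the censoring date of a subject who has some ALT values.

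**Conclusion.** The point holds as to direction. The stated rule counts unsampled time as event-free, so the numbers at risk can be too high and the probability of ALT >3xULN is equal to or below the value obtained by censoring at the last ALT. The confidence intervals rest on the same numbers at risk. The direction follows from the estimator and needs no assumption about event rates.

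The size cannot be derived from the SAP. The illustrative 5% to 31% rests entirely on the assumed share and timing of early last samples, and the true understatement may be close to zero, particularly in the Treatment phase. The FUP and post-baseline intervals are the more exposed. The SAP establishes no difference in bias between vilaprisan and group B. This is a worthwhile correction to one descriptive safety display and does not threaten the wider liver evaluation or the primary BMD analysis.

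**What to change.** In section 6.5.3.10, replace the censoring sentence so that:

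1. subjects without ALT >3xULN are censored at the date of their last ALT measurement within the interval, taken from the same laboratory source that defines the events;
2. subjects with no ALT in the interval are left out of the risk set for that interval;
3. the number left out is reported by treatment group and interval.

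The cost is a short text change, one derived date variable and one extra table row. No new data are needed, and results do not change where the last ALT already falls on the interval end.
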